2.1 Baseline comparison

Descriptive statistics: We will describe participant flow by group allocation in a flowchart. For participants included in the main analysis, we will describe background factors. Background factors will be summarised by counts (percentages), means (standard deviation) or medians (interquartile range) as appropriate. Information on the proportion with missing information will be provided.

Box 1: Background factors which will be presented by intervention and control group

Suburb (group of zones)* Age* Sex Formal education (highest completed grade) Whether signed or fingerprinted the consent form Visual classification of weight Prior chronic illness (major types: Hypertension/Diabetes) Medicine intake in the month prior to enrolment Admissions during the past 3 months
--

*All effect estimates will be presented adjusted for age and zone. For the other listed variables, they will be included as co-variates if adjusting for them changes the effect estimate by at least 10%

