1.3 Baseline Interview

Prior to enrolment a list of potentially eligible people was extracted from the HDSS databases. At the enrolment visit, information on sex and age was confirmed, and all participants were interviewed on chronic diseases, symptoms on the day of enrolment, medicine intake in the past month and admissions within the past 3 months. We aimed to have minimal physical contact. Therefore, weight was assessed using a visual scoring system, based on the field assistant's perception of the participant's bodily appearance, scoring weight from 1-10¹. The presence of a BCG and/or smallpox vaccination scar was also assessed by visual examination.

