2.6.2 Alternative analytical approaches

Due to the potential imbalance which may have resulted due to the differential refusal rates, we will in subsequent analyses use targeted maximum likelihood estimation^{2,3} (TMLE) in a re-analysis of primary and secondary outcomes. The modelling step will include the categorical variables sex, visual weight-classification (1-10), chronic illness, symptoms on the day of enrolment, medicine intake in the past month, ethnic group, whether signed or fingerprinted the consent form, and the continuous variable, age.

Specification of the models used will be guided by a machine learning algorithm (Super Learner)⁴ using both a default library of prediction models as well as a more elaborate library.

3. References

2. van der Laan MJ, Rubin D. Targeted Maximum Likelihood Learning. *The International Journal of Biostatistics* 2006; **2**(1).
3. van der Laan MJ, Rose S. Targeted Learning: Causal Inference for Observational and Experimental Data Berlin: Springer.
4. Polley EC, van der Laan MJ. Super Learner In Prediction. U.C. Berkeley Division of Biostatistics: Working Paper 266., 2010.

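### Box 1 and the later TMLE adjust for the same refusal imbalance with different baseline factors, so the main adjusted Cox model cannot include enrolment-day symptoms and the TMLE omits zone

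*SAP*

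**What the plan says.** SAP 1.6.1 reports high refusal, above all in the intervention arm. It plans a result adjusted for age and zone only, and a further result adjusted for those Box 1 factors that move the estimate for the primary outcome by more than 10%. SAP 2.6.2 gives the same refusal problem as the reason for a TMLE re-analysis, which 1.6.1 says will be reported at a later stage.

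The list in SAP 2.1 carries the title "Box 1: Background factors which will be presented by intervention and control group". Its first six entries are "Suburb (group of zones)* Age* Sex Formal education (highest completed grade) Whether signed or fingerprinted the consent form Visual classification of weight"; the remaining three are "Prior chronic illness (major types: Hypertension/Diabetes) Medicine intake in the month prior to enrolment Admissions during the past 3 months". Its footnote states: "All effect estimates will be presented adjusted for age and zone". The other factors enter only under the 10% rule.

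The TMLE list in SAP 2.6.2 runs "sex, visual weight-classification (1-10), chronic illness, symptoms on the day of enrolment, medicine intake in the past month, ethnic group", followed by the signed-or-fingerprinted consent indicator and age as a continuous variable.

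SAP 1.3 says that everyone enrolled was "interviewed on chronic diseases, symptoms on the day of enrolment, medicine intake in the past month and admissions within the past 3 months". SAP 1.2 says that houses were randomised within zones of five suburbs.

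**The concern.** Two analyses meant to deal with one imbalance would normally start from one list of baseline factors, or give a reason where they do not. Here no reason is given, and the gaps fall on factors that matter.

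- **Enrolment-day symptoms** are close to an infection outcome, and the SAP itself treats them as something to adjust for in 2.6.2. The candidates for the adjusted Cox model are limited to Box 1 (SAP 1.6.1 and Table 1), so symptoms cannot enter it. Box 1 also defines what is tabulated by arm, so the first report need not show whether the arms differed on symptoms. Ethnic group is in the same position.
- **Zone** is the randomisation stratum and is always in the Cox model, but it is not in the TMLE list. Education and admissions in the previous three months are also missing there.

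The trial has no placebo: controls receive advice only (Protocol, Intervention). Refusal depended on arm, so randomisation alone cannot be relied on to balance those enrolled. If the Cox and TMLE results then differ, a reader cannot tell whether the method or the covariates caused it.

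**Working it through.** **1. Comparison of the lists**

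| Factor | Box 1 (SAP 2.1) | TMLE (SAP 2.6.2) |
|---|---|---|
| Age | yes (5-year bands in the Cox model) | yes (continuous) |
| Sex | yes | yes |
| Visual weight | yes | yes |
| Chronic illness | yes | yes |
| Medicine in the past month | yes | yes |
| Signed or fingerprinted | yes | yes |
| Suburb/zone | yes | **no** |
| Education | yes | **no** |
| Admissions, past 3 months | yes | **no** |
| Enrolment-day symptoms | **no** | yes |
| Ethnic group | **no** | yes |

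Box 1 has 9 factors and the TMLE has 8. Six are shared, three are only in Box 1 and two are only in the TMLE. The union is 6 + 3 + 2 = 11.

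**2. Availability.** Symptoms and admissions were asked of all participants (SAP 1.3). SAP 1.3 does not list ethnic group among the interview items, but 2.6.2 plans to use it, so it must be available. Zone is known for every randomised house: 9 + 8 + 9 + 3 + 5 = 34 zones in five suburbs (SAP 1.2).

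**3. What an omitted factor could do.** The documents give neither the prevalence of symptoms by arm nor their relation to the outcome, so the values below are assumptions. For one binary factor with prevalence p1 in the OPV arm and p0 in controls, and outcome risk ratio r, a true null appears as about

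(1 + p1(r − 1)) / (1 + p0(r − 1)).

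| OPV / control prevalence | r = 1.5 | r = 2 | r = 3 |
|---|---|---|---|
| 25% / 30% | 1.125/1.150 = 0.978 | 1.25/1.30 = 0.962 | 1.50/1.60 = 0.938 |
| 20% / 30% | 1.10/1.15 = 0.957 | 1.20/1.30 = 0.923 | 1.40/1.60 = 0.875 |
| 10% / 20% | 1.05/1.10 = 0.955 | 1.10/1.20 = 0.917 | 1.20/1.40 = 0.857 |

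The range is 0.86 to 0.98. For scale, the protocol's planned fall from 10% to 7.2% corresponds to a hazard ratio of ln(0.928)/ln(0.90) = 0.71.

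**4. Would listing symptoms in Box 1 be enough?** Take the change as relative to the unadjusted hazard ratio when adjustment restores 1.00:

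- 1/0.957 = 1.045, a 4.5% change
- 1/0.923 = 1.083, an 8.3% change
- 1/0.917 = 1.091, a 9.1% change
- 1/0.875 = 1.143, a 14.3% change
- 1/0.857 = 1.167, a 16.7% change

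Only two of the nine cells, 0.875 and 0.857, pass the 10% rule. In the other seven, symptoms would be tabulated but left out of the model.

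**The case against.** The strongest reply is that the TMLE is a later re-analysis that does not determine the primary result, and a sensitivity analysis need not copy the main model's covariates. Six factors are shared. The consent-signature indicator may carry part of education, and chronic illness and medicine intake may carry part of prior admissions. Randomisation within zones balances houses on zone by design. The Box 1 footnote could be read as already covering the TMLE. People with acute current infection were not invited (SAP 1.1), which narrows the spread of enrolment-day symptoms.

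Much of this stands as a limit on size. It means that the TMLE gaps matter less than the Box 1 gaps. It does not explain why symptoms count as an adjustment factor in one analysis and cannot enter the other. Nor does it reconcile the footnote with a TMLE list that names age but not zone.

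A reader might infer more than the documents support:

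- **That vaccination scars are a further omitted confounder.** SAP 1.3 records that "The presence of a BCG and/or smallpox vaccination scar was also assessed by visual examination", but scars are in neither list, so they are not a mismatch. The SAP plans them only as effect modifiers (Table 5), and nothing suggests that they differ by arm.
- **That zone is the axis along which refusal, epidemic waves and access to care vary.** SAP 1.6.1 describes refusal by arm, SAP 2.4.2 describes waves by calendar period for the Bissau sector as a whole, and access by zone is not described. The case for zone rests on its being the stratum and on the footnote.
- **That staff screened more strictly in OPV houses and left a healthier OPV arm.** This is conceivable without blinding, but it is documented nowhere.

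**Conclusion.** The inconsistency is real and can be confirmed by reading the two lists. Enrolment-day symptoms and ethnic group are missing from Box 1, and zone, education and prior admissions are missing from the TMLE, with one shared rationale and no reason for the differences. The Box 1 gap carries more weight because it affects the first-reported adjusted result and the baseline table.

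It would go too far to say that the primary estimate is biased, or that each analysis leaves open the confounding the other was meant to close. The figures of 0.86 to 0.98 rest on assumed prevalences, assumed risk ratios and a single binary factor unrelated to the covariates already adjusted for. They run from negligible to larger than the SAP's own 10% threshold. They are not a bound: a wider gap between arms would go lower, and a gap in the opposite direction would push the estimate above 1.

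The point still deserves a change and not just a clarification. Where refusal differs by arm, adjusting for a collected baseline factor close to the outcome, and for the stratification factor, costs almost nothing and can change the estimate.

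**What to change.** 1. Add enrolment-day symptoms and ethnic group to Box 1, so that both are shown by arm.
2. Include enrolment-day symptoms in the adjusted Cox model regardless of the 10% change rule, with the coding fixed in advance. Keep the age-and-zone result alongside, as SAP 1.6.1 already plans. State plainly that this exception applies to symptoms; ethnic group would follow the same rule as the other Box 1 factors.
3. Add zone, education and admissions in the past three months to the TMLE covariates in SAP 2.6.2. If 34 zones prove too sparse, use suburb and say so.

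Both analyses then draw on the same 11 baseline factors. Any difference that is kept on purpose, such as age in bands in one and continuous in the other, should be stated with its reason.

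The cost is SAP wording and a few more parameters. No new data are needed, since every variable is already collected or already planned for use in the SAP. The change should be made before outcomes are compared by arm.

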2.2 Primary analysis of primary outcome

The rates of the primary outcome (a composite outcome of the first of death, hospitalisation for infection and/or consultation for infection at the health centre) within 6 months after enrolment will be compared in Cox proportional hazards models with time since enrolment as the underlying timescale.

The primary analysis of the primary outcome is described in more detail in table 1.

Table 1: Primary analysis of primary outcome

Population	Per-protocol population
Observation period	From: enrolment To: 183 days after enrolment Censoring: None
Failure definition	Death or first post-enrolment admission for infection and/or consultation for infection registered at a health centre.
Statistical tools	Cox-proportional hazards model, adjusted for the zone (stratification variable in the randomisation) and age. Robust standard error to adjust for same-house clustering.
Outline stata code	<pre>stset outdate, f(combinedoutcome=1) origin(dateenrol) enter(dateenrol) exit(dateenrol+183) stcox group b11.zone b50.agegroup b1.box1var1 b1.box1var2 ..., vce(cl house) Where [box1var1] [box1var2] etc. are the background factors from Box1 which affect the [group]-estimate by at least 10% Check of proportional hazards assumption¹: estat phtest, detail stphplot, adj(zone agegroup box1var box2var) strata(group)² stcox group, strata(zone agegroup box1var box2var) vce(cl house) /// tvc(group) tezp(_t)</pre>

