1.6.3 Missing data

No outcome data will be imputed. However, for a particular event, we will assume that it was not caused by an infection if no information is obtained. Some dates of events may be imprecise (e.g., unknown date of consultation or only month of event known) – such dates will be allocated to the midpoint of the range of possible dates. As all individuals are followed for mortality through the HDSS, individuals whom we were not able to contact by telephone will still contribute to the assessment of the main outcome.

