2.3 Analyses of secondary outcomes

For our secondary outcomes a) episodes with self-reported infectious disease morbidity reported through the monthly follow-up calls, b) episodes with self-reported infectious disease morbidity suspected to be caused by COVID-19 (three or more of the following: fever, cough, sore throat, extreme fatigue, loss of smell and/or taste) and f) reported consultation for infectious disease, we will analyse repeated events data sets including all individuals for whom information was obtained through the telephone follow-up.

For the separated components of the composite outcome the population depends on the outcome assessed: c) mortality is for all individuals, d) hospital admissions for all individuals for whom a telephone follow-up was conducted and e) recorded consultation for all individuals alive in the study area.

The analyses of the secondary outcomes are described in more detail in table 2, 3 and 4.

¹If we identify evidence for non-proportionality, we will still report the marginal hazard ratios, but supplement this estimate by hazard ratios for 2-3 properly selected categorical time-periods identified based on the aforementioned proportionality investigations.

² If there is indication of non-proportionality based on assessment of the log-log curves, we will test for non-proportionality by replacing the term `tezp(_t)` with `tezp(_t>s)` for specific values of `s`.

Table 2: Analyses of secondary outcomes (a, b, d, f) – reported morbidity outcomes

Population	Per-protocol population
Observation period	From: enrolment To: 183 days after enrolment Censoring: Death, Date of loss to follow-up (last telephone interview)
Failure definition	
 a) Self-reported infectious disease morbidity. b) Self-reported infectious disease morbidity suspected to be caused by COVID-19 d) Hospital admission for infectious disease f) Reported consultation for infectious disease 
Repeated events. Episodes within 2 weeks of each other will be considered as related to the same infection. Thus, a trial participant will re-enter the population-at-risk 14 days after the episode start, provided that there has been a period without reported symptoms in the meantime.

Statistical tools	Repeated Cox-proportional hazards model, adjusted for the zone (stratification variable in the randomisation), age and box1 factors. Robust standard error to adjust for same-house clustering.

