Outline stata code for analysis:	<pre>stset outdate2³, f(outcome=1) origin(dateenrol) time0(datestart) exit(censoring_date) id(study number) stcox group b11.zone b50.agegroup b1.box1var1 b1.box1var2 ..., vce(cl house)</pre> 
Where [box1var1] [box1var2] etc. are the background factors from Box1 which affect the [group]-estimate for the main outcome by more than 10%

Table 3: Analyses of secondary outcomes (c) - mortality

Population	Per-protocol population
Observation period	From: enrolment To: 183 days after enrolment Censoring: Migration
Failure definition	Death due to any cause
Statistical tools	Cox-proportional hazards model, adjusted for the zone (stratification variable in the randomisation), age and box1 factors. Robust standard error to adjust for same-house clustering.
Outline stata code for analysis:	<pre>stset outdate, f(death=1) origin(dateenrol) enter(dateenrol) exit(dateenrol+183) stcox group b11.zone b50.agegroup b1.box1var1 b1.box1var2 ..., vce(cl house)</pre> 
Where [box1var1] [box1var2] etc. are the background factors from Box1 which affect the [group]-estimate for the main outcome by at least 10%

³ Where outdate2 is the date of debut of symptoms and datestart is the date of enrolment or 14 days after a previous episode.

Table 4: Analyses of secondary outcomes (e): Recorded consultation due to infectious disease.

Population	Per-protocol population
Observation period	From: enrolment To: 183 days after enrolment Censoring: Death
Failure definition	Recorded consultation due to infectious disease. Repeated events. Episodes within 2 weeks of each other will be considered to be related to the same infection. Thus, a trial participant will re-enter the at-risk-population 14 days after the episode start, provided that there has been a period without reported symptoms in the meantime.
Statistical tools	Repeated Cox-proportional hazards model, adjusted for the zone (stratification variable in the randomisation), age and box1 factors. Robust standard error to adjust for same-house clustering.
Outline Stata code for analysis:	stset outdate2⁴, f(outcome=1) origin(dateenrol) time0(datestart) exit(censoring_date) id(study number) stcox group b11.zone b50.agegroup b1.box1var1 b1.box1var2 ..., vce(cl house) Where [box1var1] [box1var2] etc. are the background factors from Box1 which affect the [group]-estimate for the main outcome by more than 10%

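### The primary composite is analysed without censoring, so participants who migrate stay at risk to day 183, although the SAP censors deaths at migration and limits consultations to residents

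*SAP*

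**What the plan says.** For the primary composite, SAP 2.2 (Table 1) gives "From: enrolment To: 183 days after enrolment Censoring: None". Tables 5 and 6 use the same rule, and section 2.4.2 mentions only the 183-day limit for the main analyses.

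The components are treated differently when analysed alone (SAP 2.3):

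- **Death (Table 3):** "From: enrolment To: 183 days after enrolment Censoring: Migration".
- **Hospital admission (Table 2):** "Censoring: Death, Date of loss to follow-up (last telephone interview".
- **Recorded consultation:** the text gives the population as "e) recorded consultation for all individuals alive in the study area", but Table 4 gives "From: enrolment To: 183 days after enrolment Censoring: Death".

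On missing data, SAP 1.6.3 notes that mortality is followed through the HDSS and concludes that "individuals whom we were not able to contact by telephone will still contribute to the assessment of the main outcome". It does not mention migration.

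**The concern.** The composite takes its events from three sources: deaths mainly from the HDSS, admissions from telephone self-report, and consultations from the books of two local health centres. Once a participant leaves the area, the first and third sources largely stop. The SAP recognises this for each of those components separately, but not for the composite built from them, and gives no reason for the difference.

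Two things are at stake. Person-time that can hardly yield an event is counted as event-free, which distorts the hazard ratio if migration differs by arm. In addition, SAP 1.6.2 uses the components to test the robustness of the primary result, and that comparison is weakened when composite and components follow different risk-set rules. Since this is the primary analysis, two careful analysts should not be able to obtain different hazard ratios from the same SAP.

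**Working it through.** **1. Does the code settle it?** Table 1 has "stset outdate, f(combinedoutcome=1) origin(dateenrol) enter(dateenrol) exit(dateenrol+183"; Table 3 has "stset outdate, f(death=1) origin(dateenrol) enter(dateenrol) exit(dateenrol+183". Apart from the failure variable they are the same. Table 3 can censor at migration only if outdate carries the migration date; Table 1 says there is no censoring. The value of outdate for people without an event is not stated, so the code is compatible with either rule.

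**2. The plan's own figure.** Inputs from the protocol (Sample size): 3400 participants, half per arm, risks of 10% and 7.2%, a 28% reduction, 80% power, alpha 0.05. The SAP makes tests two-sided. The formula is not named.

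- Expected events: 1700 × (0.10 + 0.072) = 292.4.
- Schoenfeld power at HR 0.72: Φ(√292.4 × |ln 0.72| / 2 − 1.960) = 80.2%.
- Required events: 291, so N = 291 / 0.086 = 3384.

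The stated 80% is reproduced, with no allowance for migration or loss. (Comparing two proportions gives 81.4% with continuity correction and 83.0% without.)

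**3. Effect of not censoring movers.** The documents give no migration rate, so every L below is an assumption. Let a share L of an arm leave uniformly over 183 days, with all later events missed. On average half of the movers' events are lost, so recorded risk ≈ true risk × (1 − L/2), and the HR is multiplied by about (1 − L_OPV/2) / (1 − L_control/2).

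| Control / OPV migration | Multiplier | Arms reversed |
|---|---|---|
| equal (5%, 10% or 20% each) | 1.00 | 1.00 |
| 5% / 10% | 0.950/0.975 = 0.974 | 1.026 |
| 5% / 15% | 0.925/0.975 = 0.949 | 1.054 |
| 10% / 20% | 0.900/0.950 = 0.947 | 1.056 |

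At the extremes, a true HR of 1.00 reads about 0.95 or 1.06, and 0.72 reads about 0.68 or 0.76.

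A Cox simulation (1.5 million per arm, exponential event times, 10% control risk) agrees. Comparing the uncensored with the censored estimate gave ratios of 0.974, about 0.949 and 0.947, reversed 1.027, 1.055 and 1.056, and within 0.1% of 1 for equal loss. Where departure was unrelated to risk, censoring at departure recovered the HR in every scenario.

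**4. Events and power.** With equal loss of 5%, 10% or 20%, events are 292.4 × (1 − L/2) = 285, 278 or 263, and power at HR 0.72 is 79.2%, 78.2% or 75.9%. Events that are never seen are lost under either rule, so under this assumption censoring costs no further events.

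**5. Telephone non-contact is a smaller matter.** If a share c of events after loss of contact is still captured by the HDSS or the health centres, the multiplier is (1 − (1−c)L_OPV/2) / (1 − (1−c)L_control/2). For 10% against 20% losing contact, c = 0.5 gives 0.950/0.975 = 0.974 and c = 0.9 gives 0.990/0.995 = 0.995: a shift of about 2.6% down to 0.5%. Both c and the loss shares are assumptions.

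**The case against.** A composite with two passive sources can reasonably have a different censoring rule from outcomes known only by telephone, and 1.6.3 shows that keeping people without telephone contact was deliberate. That stands. A reader might infer that everyone who cannot be reached is simply counted as event-free. The documents do not support this: deaths still come from the HDSS and consultations from the health-centre books (SAP 1.4.2), so only self-reported admissions are lost. A single missed call need not lose even those, because each interview asks about the time since the last one and a relative may answer (SAP 1.4.1).

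Nor is it certain that movers are wholly unobserved. The protocol has staff collect several telephone numbers, and calls do not depend on residence. Missing every event after a move is therefore a worst case.

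A reader might also infer that the primary HR is biased, because acceptance differed by arm. SAP 1.6.1 reports higher refusal in the intervention arm at enrolment; it says nothing about migration or loss afterwards, and equal loss leaves the HR essentially unchanged.

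Finally, for consultations the conflict is with the text of 2.3, not with Table 4, which has no migration rule either. This is correct, but it adds a second inconsistency and does not excuse the first. None of these arguments explains why migration ends follow-up for death alone but not for death within the composite.

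**Conclusion.** The inconsistency is certain. Tables 1, 5 and 6 keep migrants at risk to day 183; Table 3 and the text of 2.3 do not; Table 4 contradicts 2.3; and the undefined outdate leaves the primary risk set open to two readings.

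Bias is possible but not demonstrated. Its size rests on three assumptions: the migration share in each arm, departures spread evenly over follow-up, and no events captured after a move. On these, the HR shifts by about 3% for a 5-point difference between arms and about 5-6% for a 10-point difference, towards apparent benefit if more of the OPV arm leaves. That is modest beside the 28% reduction the trial was sized for. The case for acting rests on the unsettled definition of the primary analysis, not on a proven distortion.

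**What to change.** - **Define outdate.** It is the date of the first event or, without an event, the earlier of migration out of the HDSS area and enrolment + 183 days. Say that moves within the HDSS area do not end follow-up.
- **Tables 1, 5 and 6:** replace the absence of censoring with that rule.
- **Table 4:** censor at death or migration, in line with the text of 2.3.
- **Telephone non-contact:** keep the 1.6.3 rule in the primary analysis. Add one sensitivity analysis that censors all components, deaths included, at the last successful telephone interview. Keeping later deaths while dropping survivors' time over the same period would inflate death rates. Count a call in which a relative gives the information as successful; otherwise every death would fall after the participant's last interview.
- **Reporting:** give migration and telephone contact by arm.

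The cost is SAP wording and one redefined variable, using migration and interview dates that the SAP's other tables already require. Person-time falls slightly. Events and power are essentially unchanged, except that any event learned of after a move would no longer count. Censoring at migration also assumes that leaving is unrelated to risk within arm and covariates, which should be stated.
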